11.1.1. Immunogenicity Endpoints

- Incidence of anti-drug antibodies and neutralizing antibodies (NAb) to ALXN1830
- Quantitative assessment of immunogenicity between Japanese and non-Japanese healthy participants

11.1.2. Analysis of the Endpoints

The endpoint regarding the quantitative assessment of immunogenicity between Japanese and non-Japanese healthy participants cannot be analyzed due to early termination of the study.

ADA and NAb data reporting

- Incidence, titer, duration, time to detection, pre-existing ADA
- PK concentration or parameter by immunogenicity response
- PD response by immunogenicity response
- Individual PK data listing or spaghetti plots with ADA category overlaid.
- For ADA categories and participants, summary of individual plots of PK, PD, ADA titer, and NAb time course to better understand the clinical impact of immunogenicity at a subject level.

12. Safety

The population used for safety analyses will be the Safety Set.

Safety analyses will include an analysis of all treatment-emergent adverse events (TEAEs), SAEs, AESIs, ECGs, clinical laboratory data, physical examinations, and vital sign measurements using descriptive statistics.

No inferential statistical analyses are planned on the safety parameters of this study.

12.1. Adverse Events / Adverse Drug Reactions

AEs for all participants in the Safety Set will be included in the AE summaries.

Adverse events will be summarized by system organ class (SOC) and preferred term (PT) for each treatment and overall, based on the MedDRA dictionary version 23.1.

If the relationship to study drug is missing for TEAEs, then the relationship will be counted as related to study product for the summary tables. Missing severity for TEAEs will be counted as Grade 3.

Pretreatment AEs are defined as AEs that were reported or worsened after signing the ICF up to the start of study drug dosing. Treatment-emergent AEs are defined as AEs that were reported or worsened on or after the start of study drug dosing through the safety follow-up visit.

If the start date of an AE is partially or completely missing, the date will be compared as far as possible with the date of the start of administration of study drug. The AE will be assumed to be treatment-emergent if it cannot be definitively shown that the AE did not occur or increase in severity during the treatment period (worst case approach). The following general rules will be used:

- If the start day is missing but the start month and year are complete, an AE will not be considered as being treatment-emergent only if the start month/year is before the month/year of the first study drug administration.
- If the start day and month are missing but the start year is complete, an AE will not be considered as being treatment-emergent only if the start year is before the year of the first study drug administration.
- If the start date is completely missing, an AE will be considered treatment-emergent unless the stop date is before the first study drug administration.

Duration will be calculated for AEs that resolve as the difference between the resolution date and onset date plus 1 and expressed in days. Should an AE have a short duration (*i.e.* < 24 hours), the duration will be calculated as the difference between the resolution time and the onset time.

Adverse events of special interest are defined as any IRR equal to or higher than Grade 3; or any IRR that may jeopardize the participant and requires immediate intervention to prevent it from leading to severe outcomes. Potential cases of any delayed hypersensitivity reactions, equal to or higher than Grade 2.

The summary tables will include the number of participants and the number of events. Percentages will be based on the number of participants and on the number of events. For summaries by SOC and PT, a participant will be counted once at the SOC level and once at each PT within the SOC level.

Sponsor: Alexion Pharmaceuticals, Inc.; Protocol No.: ALXN1830-HV-108

For summaries by SOC, PT, and maximum severity, a participant will be counted once at the highest severity level for which the event occurred at the SOC level and the highest severity level for each unique PT within that SOC level. Therefore, participants may only contribute once to each PT and once to each SOC level.

The summaries presenting frequency of AEs by SOC and PT will be ordered by overall descending frequency of SOC and then, within a SOC, by overall descending frequency of PT.

The following tables will be provided:

- An overall summary of the number and percentage of participants reporting TEAEs, serious TEAEs (TESAEs), TEAEs resulting in death, TEAEs of special interest, TEAEs leading to study drug discontinuation, TESAEs leading study drug discontinuation, TEAEs by relationship and TEAEs by toxicity grade;
- TEAEs overall by system organ class and preferred term;
- TEAEs by maximum toxicity grade, overall and by system organ class and preferred term;
- TEAEs by toxicity grade, overall and by system organ class and preferred term;
- TEAEs by maximum relationship to study medication, overall and by system organ class and preferred term;
- TEAEs by relationship to study medication, overall and by system organ class and preferred term;
- TEAEs by system organ class sorted by decreasing frequency; TEAEs by preferred term sorted by decreasing frequency;
- Related TEAEs by preferred term sorted by decreasing frequency;
- TESAEs, overall and by system organ class and preferred term;
- TESAEs by maximum relationship to study medication, overall and by system organ class and preferred term;
- TESAEs by relationship to study medication, overall and by system organ class and preferred term:
- Non-serious TEAEs overall and by system organ class and preferred term;
- TEAEs leading to study drug discontinuation, overall and by system organ class and preferred term;
- TEAEs leading to death, overall and by system organ class and preferred term;
- TEAEs of special interest, overall and by system organ class and preferred term;

Only TEAEs will be included in the summary tables, however separate listings for treatment-emergent and non-treatment-emergent AEs will be generated. Additional listings will be provided for deaths, AESIs, serious AEs and Adverse Events Leading to Study Drug Discontinuation.

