PD blood sampling - IgG subtypes 1-4	X	X	X	X	X	X	X	X	X	X	X	
PD blood sampling – CIC	X	X	X	X	X	X	X	X	X	X	X	
Immunogenicity blood sampling - ADA						X		X	X		X	
FcRn occupancy	X	X		X			X	X				
Biochemistry f		X						X			X	
Coagulation		X									X	
Hematology		X						X	X		X	
Exploratory biomarker sample		X									X	
Urinalysis		Xg							X		X	
Vital signs h	X	X	X	X	X	X	X	X	X	X	X	
12-lead ECG (triplicate)	X	X	X	X	X	X					X	
Concomitant medications			•	•	←Mon	itor continuo	ously (after I	CF is signed	at Screenin	g)→	•	
Adverse events					←Mon	itor continuo	ously (after I	CF is signed	at Screenin	g)→		

<sup>a Participant will be discharged from the CRU after completing all Day 9, 16, and 29 assessments.

<sup>b Serum pregnancy test at Screening and Day -1 and urine pregnancy test for all other timepoints in CRU and OP.

<sup>c For the Day 85 Visit, dispense a urine pregnancy test kit for the Day 113 Follow-up Phone Call. For an ET Visit, dispense urine pregnancy test kits to allow monthly testing for 3 months after the last dose.

<sup>d Participants will be requested to take a urine pregnancy test at home at approximately Day 113, or, if ET, monthly for 3 months after the last dose; the site will solicit results, along with adverse events and concomitant medications, via phone call.

<sup>e Full PE at screening and symptom directed PE thereafter.

<sup>f Fasting, due to lipid panel. Note: lipid panel is not performed at Screening.

<sup>g Visit window (hours) is not applicable for urinalysis.

<sup>h Including temperature, respiratory rate, and pulse oximetry.

Abbreviations: ADA = antidrug antibodies; BMI = body mass index; CIC = circulating immune complexes; CRU = Clinical Research Unit; ECG = electrocardiogram; ET = early termination; FcRn = neonatal crystallizable fragment receptor; h = hours; ICF = informed consent form; Ig = immunoglobulin; NA = not applicable; OP = outpatient; PD = pharmacodynamic(s); PE = physical examination; PK = pharmacokinetic(s); WOCBP = women of childbearing potential.

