#### 4. STUDY DESIGN

# 4.1. Overall Design

This is a Phase 1 study in up to a maximum of 48 healthy adult participants (36 on active treatment, 12 on PBO). The study will consist of 2 SAD (Cohorts 1 and 2) and 4 MAD cohorts (Cohorts 3 to 6). Cohort 6 will enroll Japanese participants. Eight participants will be randomly assigned in a 6:2 ratio in each of the 6 cohorts to receive either single or multiple SC doses of ALXN1830 (n = 6 per cohort) or single or multiple doses of PBO (n = 2 per cohort). The planned study duration is approximately 124 days for Cohorts 1 and 2: up to 60 days for screening and approximately 64 days for dosing and follow-up; 201 days for Cohort 3: up to 60 days for screening and approximately 141 days for dosing and follow-up; and 148 days for Cohorts 4 to 6: 60 days for screening and approximately 88 days for dosing and follow-up. Participants will be admitted to an inpatient facility during the dosing and follow-up period as shown in Section 1.3.

Initially, the first 4 participants randomized to each cohort will be dosed with 3 participants on active treatment and 1 participant on PBO. The dosing will be staggered, with an interval of at least 3 days for the SAD cohorts and at least 7 days for the MAD cohorts, before dosing the rest of the participants in the cohort. The shorter interval of staggered dosing for the SAD cohorts compared to the MAD cohorts is considered appropriate as the expected PK exposure of the ALXN1830 SC doses will be a fraction of that of the IV dose demonstrated to be safe and well tolerated in previous IV studies. The reduction of IgG after a single SC dose will be similar to the observed IgG reduction in previous IV studies; and in general, there will be low risk of immunogenicity and IRRs after a single dose. See Section 4.3 for details regarding expected PK exposures and IgG reduction. All participants will be observed during the drug administration and for 2 hours after dosing for safety and participants will be encouraged to report any discomfort immediately, especially within 24 hours post dosing. At no time will more than 4 participants per cohort be dosed on a given day.

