Participants will be randomly assigned in a 6:2 ratio to each of the 6 cohorts to receive either single or multiple doses of ALXN1830 SC (n = 6 per cohort) or single or multiple doses of PBO (n = 2 per cohort). The planned dose and dose regimens are shown in Table 1. The planned study duration is approximately 124 days for Cohorts 1 and 2: up to 60 days for screening and approximately 64 days for dosing and follow-up; 201 days for Cohort 3: up to 60 days for screening and approximately 141 days for dosing and follow-up; and 148 days for Cohorts 4 to 6: 60 days for screening and approximately 88 days for dosing and follow-up. Participants will be admitted to an inpatient facility during the dosing and follow-up period as shown in the schedule of activities (SoA) in Protocol Section 1.3 . The study design is presented in Figure 1.

Table 1: Planned Dose and Dose Regimens in Healthy Participants

Cohort No.	Regimen/Route of Administration	Study Drug (N)
1	Single dose SC	Placebo (n = 2) or ALXN1830 1500 mg (n = 6)
2	Single dose SC	Placebo (n = 2) or ALXN1830 2250 mg (n = 6)
3	Multiple dose (12 doses qw) SC	Placebo (n = 2) or ALXN1830 750 mg (n = 6)
4	Multiple dose (4 doses qw) SC	Placebo (n = 2) or ALXN1830 1500 mg (n = 6)
5	Multiple dose (4 doses qw) SC	Placebo (n = 2) or ALXN1830 2250 mg (n = 6)
6ª	Multiple dose (4 doses qw) SC Japanese healthy participants	Placebo (n = 2) or ALXN1830 HTD (n = 6)

^a Healthy, Japanese participants enrolled in Cohort 6 will be dosed according to the HTD established in the non-Japanese cohorts. This cohort was not achieved due to early termination of the study. Abbreviations: qw = weekly; SC = subcutaneous; HTD = highest tolerated dose.

Figure 1: Study Design Schematic

Abbreviations: D = day; HTD = highest tolerated dose; MAD = multiple ascending dose; PBO = placebo; qw = weekly; SAD = single ascending dose; SC = subcutaneous; SRC = Safety Review Committee.

Progression to the next dosing cohort will be gated by review of initial dosing data by an SRC consisting of the Investigator, and Alexion Safety Physician, Medical Monitor, Study Statistician, and Clinical Pharmacologist.

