7.1. General Methods

- In general, descriptive statistics for continuous variables will include number of non-missing values, arithmetic mean, SD, median,interquartile range (IQR), Q1, Q3, minimum, and maximum. Categorical variables will be summarized using percentages and frequency counts. Descriptive statistics and percentages and frequency counts will be summarized by treatment, and period, where appropriate.
- For the summary statistics of all continuous variables unless otherwise specified, minimum and
 maximum will be presented to the same number of decimal places as the raw data. Mean, median,
 Q1, Q3, and IQR will be presented to one more decimal places than the raw data, and SD will be
 presented to two more decimal places than the raw data.
- All statistical analyses will be conducted using SAS® for Windows® Version 9.4 or higher.
- All relevant participant data will be included in listings. All participants entered into the database will be included in participant data listings.

In general, tables will be split over multiple pages, with the following columns:

- Cohort 1: SAD ALXN1830 1500 mg
- Cohort 2: SAD ALXN1830 2250 mg
- Cohort 3: MAD ALXN1830 750 mg QW x 12
- Cohort 4: MAD ALXN1830 1500 mg QW x 4
- Cohort 5: MAD ALXN1830 2250 mg QW x 4
- All Cohorts Placebo
- All Cohorts Total

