Laboratory parameter values will be graded according to the National Cancer Institute Common Terminology Criteria for Adverse Events (CTCAE).

All summaries will be based on results in SI (standard international system of units) units and will be

output in the order listed above.

Toxicity grading following the NCI CTCAE grades version 5.0 will also be derived for laboratory variables where applicable (see list below). Note, where gradings require investigator/clinical input, this will not be considered and only the numeric criteria will be used for the assignments. If this results in the criteria for more than one grade being met, the highest (worst) CTCAE grade will be assigned. For creatinine only, the criteria based on the upper limit of normal (ULN) will be used (changes compared to the baseline value will not be used), eg, CTCAE defines Grade 1 as > ULN - 1.5 x ULN or > 1 - 1.5 x baseline. Only the ULN – 1.5 x ULN criterion will be used (and not the baseline criterion).

The following parameters are CTCAE gradable:

- Clincal Chemistry: Alanine aminotransferase albumin, alkaline phosphatase, aspartate aminotransferase, total bilirubin, creatinine, gamma-glutamyl transferase, glucose (only do the grading the hypoglycemia, no grading for hyperglycemia), creatine kinase.
- **Hematology**: Absolute neutrophil count (neutrophil), total leukocytes (Leukocytes), hemoglobin (only do the grading for anemia, no grading for hemoglobin increased), platelet count, lymphocyte.
- Coagulation:International normalized ratio.

Actual values and changes from baseline in clinical chemistry, hematology and coagulation, will be summarized by treatment.

Shift tables for clinical chemistry, hematology, and coagulation from baseline CTCAE toxicity for each visit and to the maximum grade on treatment for each parameter will be provided. Participants with both a non-missing baseline and at least one non-missing post-baseline grade will be included in the shift tables. Unscheduled data will be included in the worst case across all scheduled and unscheduled visits after the first dose of study treatment. This means that if there are CTCAE grades derived from both unscheduled and scheduled visits data per test per participant then the highest grade will be summarized.

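### TEAE and worst-case chemistry and hematology tables set 750 mg (12 infusions, Day 141) beside 1500 and 2250 mg (4 infusions, Day 85) with no matched window, so a dose trend against 750 mg can be attenuated, masked or reversed

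*SAP*

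**What the plan says.** SAP 7.1 gives each active cohort its own table column, among them "Cohort 3: MAD ALXN1830 750 mg QW x 12", "Cohort 4: MAD ALXN1830 1500 mg QW x 4" and "Cohort 5: MAD ALXN1830 2250 mg QW x 4". SAP 12.1 then says: "Adverse events will be summarized by system organ class (SOC) and preferred term (PT) for each treatment and overall". An event counts as treatment-emergent from the start of dosing through the safety follow-up visit, and the tables show numbers and percentages of participants and of events.

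The length of that period depends on the cohort. SAP 4.1 gives "201 days for Cohort 3: up to 60 days for screening and approximately 141 days for dosing and follow-up"; Protocol 4.1 gives "148 days for Cohorts 4 to 6: 60 days for screening and approximately 88 days for dosing and follow-up". The schedule in Protocol 1.3 puts the last clinic visit for Cohorts 4 to 6 at Day 85, not 88: "For the Day 85 Visit, dispense a urine pregnancy test kit for the Day 113 Follow-up Phone Call".

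For laboratory data, SAP 12.2 plans CTCAE shifts at each visit and to the maximum grade. For the latter: "Unscheduled data will be included in the worst case across all scheduled and unscheduled visits after the first dose of study treatment". Tests that cannot be graded get a shift to the overall worst post-baseline category. The exposure summary in SAP 8.7 covers milligrams, volume and interruptions, but not time.

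**The concern.** The primary objective is the safety and tolerability of single and multiple doses. SAP 4.1 reports that Cohort 2 has only 2 participants and Cohort 6 none, so Cohorts 3, 4 and 5 carry most of the evidence by dose. A reader will look across those three columns. The lowest dose has three times the infusions and the longest follow-up, so it has more opportunity to record an event or an out-of-range value. Dose is confounded with exposure in the direction that can hide a dose effect against 750 mg.

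Infusion-linked events are the ones to expect. Protocol 2.3 reports 6 earlier infusion-related reactions, and headache in all participants at multiple 20 mg/kg IV doses. For such events, 12 against 4 infusions is the relevant contrast.

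Elsewhere the plan does match time. SAP 9.2 derives PK parameters on Days 1 and 22 in all three cohorts, and SAP 9.5 plots troughs over Days 8 to 22. The AE and worst-case laboratory tables have no such version.

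**Working it through.** **1. The plan's own durations.** The 12th weekly dose falls on Day 1 + 7×11 = 78. Day 78 + 63 = Day 141, and 60 + 141 = 201 days, as stated for Cohort 3. The 4th dose falls on Day 1 + 7×3 = 22, and Day 22 + 63 = Day 85. The stated 148 days is 60 + 88, whereas the schedule gives 60 + 85 = 145.

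**2. Opportunity to record events**, counted from Protocol 1.3, Tables 4 to 12:

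| | Cohort 3 | Cohorts 4 and 5 | Ratio |
|---|---|---|---|
| Infusions | 12 | 4 | 3.00 |
| Last clinic visit (day) | 141 | 85 | 1.66 |
| Same, using 88 days | 141 | 88 | 1.60 |
| Follow-up phone call (day) | 169 | 113 | 1.50 |
| Post-dose chemistry draws | 16 | 6 | 2.67 |
| Post-dose hematology draws | 20 | 11 | 1.82 |
| Post-dose coagulation draws | 3 | 3 | 1.00 |

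Chemistry days are 4, 8, 14, 21, 25, 35, 42, 49, 56, 63, 70, 77, 81, 85, 113 and 141 in Cohort 3, and 2, 14, 21, 25, 50 and 85 in Cohorts 4 and 5. The imbalance remains whether the safety follow-up visit means the last clinic visit or the phone call.

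**3. No dose effect, equal risk p per infusion.** The chance of at least one event is 1 − (1 − p)^k for k infusions. The documents give no p, so a range is assumed.

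| p | 750 mg (k = 12) | 1500 or 2250 mg (k = 4) |
|---|---|---|
| 2% | 21.5% | 7.8% |
| 5% | 46.0% | 18.5% |
| 10% | 71.8% | 34.4% |
| 20% | 93.1% | 59.0% |

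With 6 active participants per cohort and two independent binomials, 750 mg shows the higher count than one higher-dose cohort in 77% (p = 5%) to 86% (p = 10%) of trials.

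**4. No dose effect, equal daily hazard.** An assumed 30% by Day 85 becomes 1 − 0.70^(141/85) = 44.7% by Day 141.

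**5. A real dose effect.** Let the higher dose have r times the 750 mg hazard per infusion.
- r = 2, with p = 5% to 10% at 750 mg: the 750 mg count is still the higher in 56% to 60% of trials.
- r = 3, with p = 5%: 46.0% against 46.0%. The effect vanishes from the full-study table.
- Hazard per infusion proportional to dose: cumulative hazards at 750, 1500 and 2250 mg are 12×1 : 4×2 : 4×3 = 12 : 8 : 12. The trend is reversed at 1500 mg and masked at 2250 mg.
- Hazard per day proportional to dose: 141×1 : 85×2 : 85×3 = 141 : 170 : 255, or 1 : 1.21 : 1.81. The trend is attenuated but keeps its direction.

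**6. Worst-case laboratory rows.** With an assumed 2% to 5% chance of an abnormal value per draw and independent draws, at least one flag per chemistry test is expected in 27.6% v 11.4% to 56.0% v 26.5%, and per hematology test in 33.2% v 19.9% to 64.2% v 43.1%. Correlation within a person would narrow these gaps.

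**7. A common window.** From Day 1 to before the Day 29 dose, all three cohorts have 4 infusions and 28 days. Over Days 1 to 28, draws are 5 v 4 for chemistry and 7 v 8 for hematology. Counting Cohort 3's Day 29 predose hematology sample makes it 8 v 8. Equal risk now gives equal expected incidence (18.5% each at p = 5%). With r = 3 and p = 5% the window gives 18.5% against 46.0%, and the 750 mg count is the higher in 8% of trials instead of 39%.

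**The case against.** The strongest reply is that safety is descriptive by design. There is no hypothesis, no safety inference and no planned AE dose-trend analysis. Protocol 4.3 makes Cohort 3 longer on purpose, to study immunogenicity and safety over longer administration. Column headers show the regimen, SAP 8.1 tabulates study duration, and all events are listed, so with 6 active participants per cohort a reader can check onset days. All of this stands, and it makes the matter one of presentation. It does not remove the confounding: no planned table gives TEAE incidence over matched exposure.

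The size also depends on assumed rates. Protocol 8.2.9 lists infusion site reactions as AEs only if they last more than 24 hours, and Protocol 7.2.2 ends dosing after severe or serious reactions. A constant risk over 12 infusions is therefore a simplification, and early stopping in Cohort 3 would shrink the imbalance.

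A reader might infer several stronger points that the documents do not support:
- *Observation falls at every dose step.* Cohorts 4 and 5 share one schedule; only contrasts with 750 mg are affected.
- *All laboratory displays are affected.* SAP 12.2 also plans CTCAE shifts by visit, which can be read at matched days, and coagulation has 3 post-dose draws in each regimen.
- *Dose escalation rests on these tables.* Protocol Table 15 sets the minimum immunoglobulin data for the multiple-dose steps at Day 22 of the preceding cohort.

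**Conclusion.** The concern holds for two displays: the full-study TEAE tables, and the worst-case chemistry and hematology shift rows, when 750 mg is compared with 1500 or 2250 mg. At equal risk per infusion or per day, the 750 mg column is expected to show more participants with events. At an assumed 5% to 10% per infusion the gap is 46.0% v 18.5% to 71.8% v 34.4%.

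It would be too strong to say that a dose trend is necessarily masked or reversed. In expectation, full masking needs a true hazard ratio near 3 per infusion, or near 1.66 per day. A smaller true effect can be reversed and a larger one keeps its direction. Events tied only to the first dose are not biased.

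The schedule facts come from the documents. The event rates are assumptions, and the calculation takes Cohorts 3 to 5 as planned; the SAP reports early termination but gives shortfalls only for Cohorts 2 and 6. The change is worth making because it is cheap and concerns the primary safety tables.

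**What to change.** In SAP 12.1 and 12.2, add a set of tables for Cohorts 3, 4 and 5 limited to event onset or sample from first dose to before the Day 29 dose:
- TEAEs overall and by SOC and PT;
- related TEAEs;
- TEAEs by maximum grade;
- worst-case chemistry and hematology shifts.

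Only Cohort 3 is dosed on Day 29, so state the cut for Cohorts 4 and 5 in days, and say whether the Cohort 3 Day 29 predose sample counts. A cut at Day 85 would not serve, because Cohort 3 has had all 12 infusions by then.

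Use these tables as the matched-exposure view when 750 mg is compared with the higher doses. They should not become the only dose comparison, because delayed hypersensitivity is an AESI and may appear after Day 28. Keep the full-study tables for later and delayed events and for Cohort 3's long-term aim. Events per participant-month are optional, since they do not equalize infusion density. In the same edit, define the safety follow-up visit that closes the TEAE period, and reconcile 88 days with Day 85.

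The cost is a few extra tables from dates already collected. The common window leaves out later events, which remain in the full-study tables.

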#### 8.3.1. Time Period and Frequency for Collecting AE and SAE Information

All AEs and SAEs will be collected from the signing of the ICF until the follow-up visit at the time points specified in the SoA (Section 1.3).

All SAEs will be recorded and reported to Alexion or the designee immediately and under no circumstance should this exceed 24 hours, as indicated in Section 10.3. The Investigator will submit any updated SAE data to Alexion within 24 hours of it being available.

Investigators are not obligated to actively seek AEs or SAE data after conclusion of the study participation. However, if the Investigator learns of any SAE, including a death, at any time after a participant has been discharged from the study, and he/she considers the event to be reasonably related to the study drug or study participation, the Investigator must promptly notify Alexion.

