#### 9.4.1. Safety Analyses

All safety analyses will be performed on the Safety set.

Safety analyses will include an analysis of all treatment-emergent adverse events (TEAEs), SAEs, AESIs, ECGs, clinical laboratory data, physical examinations, and vital sign measurements using descriptive statistics. No inferential statistical analyses are planned on the safety parameters of this study. Clinical AEs will be coded according to MedDRA Version 21.1 or higher; AEs will be graded using the National Cancer Institute Common Terminology Criteria for Adverse Events (CTCAE), Version 5.0 or higher. AEs will be classified as pretreatment or treatment-emergent as follows:

**Pretreatment AEs** are defined as AEs that were reported or worsened after signing the ICF up to the start of study drug dosing.

**Treatment-emergent AEs** are defined as AEs that were reported or worsened on or after the start of study drug dosing through the Safety Follow-up Visit.

Only TEAEs will be summarized. The number and percentage of participants experiencing a TEAE will be summarized, by System Organ Class and Preferred Term for each cohort, by relationship to study drug, and by severity of the AE. Serious AEs and TEAEs resulting in study drug discontinuation will be listed. Some rules that will apply to the summarization of AEs are (1) a participant with multiple occurrences of the same AE or a continuing AE will only be counted once; (2) only the maximum severity level will be presented in the severity summary; and (3) only the worst relationship level will be presented in the relationship summary.

All statistical analyses of laboratory values will be performed using SI units. Changes from baseline in vital sign measurements and laboratory assessments (eg, chemistry, hematology, and urinalysis) at each scheduled time point will be summarized by cohort. Laboratory parameter values will be graded according to the CTCAE. Shift tables by cohort will be produced for these laboratory parameters. These tables will summarize the number of participants with each baseline grade relative to the reference ranges and changes to the worst highest grade assessed post-dose during the study.

The ECG parameters will be measured at the specified time points, including heart rate, PR, RR QRS, QT, and QTcF intervals. The average of the triplicate ECG readings at the time points collected will be calculated, and changes from pretreatment baseline values will be assessed by each cohort.

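### The TEAE definition turns on when an AE was reported, but the SAP's partial-date rules turn on when it started; read literally, a fully dated pre-dose AE first mentioned after dosing would count as a TEAE

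*SAP*

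**What the plan says.** The treatment-emergent definition in SAP 12.1 is that "Treatment-emergent AEs are defined as AEs that were reported or worsened on or after the start of study drug dosing". Protocol 9.4.1 has the same test: TEAEs "are defined as AEs that were reported or worsened on or after the start of study drug dosing through the Safety Follow-up Visit". The complementary class uses the same verb: "Pretreatment AEs are defined as AEs that were reported or worsened after signing the ICF up to the start of study drug dosing". None of these sentences mentions onset.

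SAP 12.1 then turns to incomplete dates: "If the start date of an AE is partially or completely missing, the date will be compared as far as possible" with the start of study drug administration. The governing principle is stated as "The AE will be assumed to be treatment-emergent if it cannot be definitively shown that the AE did not occur or increase in severity" during treatment. Three rules follow:

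- Start day missing: not treatment-emergent only if the start month and year precede those of the first dose.
- Start day and month missing: not treatment-emergent only if the start year precedes that of the first dose.
- Start date wholly missing: treatment-emergent unless the stop date precedes the first dose.

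On collection, Protocol 8.3.1 states that "All AEs and SAEs will be collected from the signing of the ICF until the follow-up visit". Screening can run from Day -60 to Day -2, with admission on Day -1 (Protocol 1.3). TEAE incidence and relatedness are part of the primary endpoint (SAP 5.1). Summary tables contain TEAEs only, and other AEs are listed (SAP 12.1; Protocol 9.4.1).

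**The concern.** The date on which an AE is reported is not the date on which it began. An AE can start and end during outpatient screening and be mentioned for the first time during the daily contact that follows dosing. Whether it is treatment-emergent should not depend on when the participant happened to mention it.

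The start-date rules in SAP 12.1 apply only when the start date is partly or wholly missing. For an AE with complete dates, the definition sentence is the only rule given, and it refers to reporting. A programmer who follows it and one who extends the start-date logic to complete dates could produce different primary-endpoint tables, each with support in the text. An AE with fully known pre-dose dates could also be classified less accurately than one with missing dates.

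Protocol 10.3.1 adds to the ambiguity: a condition first detected after dosing counts as an AE even if it may have existed before the study.

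**Working it through.** The plan states no figure to reproduce: there is no formal sample size, and no inference on safety is planned. The check is textual, followed by simple arithmetic.

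**Step 1. One event under each rule.** Take a headache that starts on Day -6, resolves on Day -5, does not worsen, and is first mentioned on Day 3.

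| What is recorded | Rule applied | Result |
|---|---|---|
| Start and stop dates complete | Definition read literally (report on Day 3 is after dosing) | TEAE |
| Start date wholly missing, stop Day -5 | Wholly-missing rule (stop precedes first dose) | Not a TEAE |
| Start day missing, start month before the month of first dose | Missing-day rule | Not a TEAE |
| Start and stop dates complete | Onset rule (start before first dose, no worsening) | Not a TEAE |

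The third row applies only if the month changes between Day -6 and Day 1. Rows 1 and 2 conflict without that condition.

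**Step 2. Effect of one misclassified participant.** Shift = 1/n, where n is the column's denominator.

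- Active, full cohort: n = 6 (SAP Table 1), so 1/6 = 16.7 points.
- Placebo: SAP 7.1 pools placebo into one column. The plan was 6 × 2 = 12, so 1/12 = 8.3 points. SAP 4.1 reports 2 participants in Cohort 2 and none in Cohort 6. Assuming Cohorts 1, 3, 4 and 5 filled at 6:2, placebo is 4 × 2 = 8, plus 0 to 2 from Cohort 2. That gives 1/10 = 10 points to 1/8 = 12.5 points.
- Cohort 2 active: with one or two active participants, one event is 100 or 50 points. A percentage on that base says little in any case.

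These are maxima. SAP 12.1 counts a participant once per SOC and once per PT, so a row moves only if the misclassified event is that participant's only TEAE in it.

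**Step 3. Frequency.** The documents give no rate. Purely as an assumption, let each participant have probability p of at least one such AE. The chance of at least one affected participant in a six-participant arm is 1 − (1 − p)^6:

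- p = 1%: 5.9%
- p = 5%: 26.5%
- p = 10%: 46.9%

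The result follows the assumed p and is not evidence of a likely rate.

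**The case against.** The strongest reply is that this is loose wording around a single intended rule. A fallback for missing start dates makes sense only if start date is the main criterion. The stated principle asks whether "it cannot be definitively shown that the AE did not occur or increase in severity during the treatment period", AE duration is computed from onset, and neither document has a rule that uses a report date. The documents also use reporting to mean having an event: SAP 12.1 counts participants reporting TEAEs where Protocol 9.4.1 counts participants experiencing one. This carries weight. It makes onset the likely intention, and if the tables are programmed that way no error occurs. It does not change what the definition says for complete dates.

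The reach is also limited:

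- AEs are monitored from consent, and medical history and eligibility are revisited at the Day -1 admission, so most screening events should be known before dosing.
- An event with known pre-dose dates lacks a plausible temporal relationship, which is a criterion for a not-related assessment in Protocol 10.3.3. It should therefore stay out of the related-TEAE tables, unless relationship is missing, in which case SAP 12.1 counts it as related.
- Safety analysis is descriptive, and the stopping rules in Protocol 7.2.2 refer to adverse reactions and infusion-related reactions, not TEAE counts.
- The error adds events and hides none.

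These points limit the size of the problem. They do not remove the inconsistency.

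**Conclusion.** The definition of a primary-endpoint class is wrong as written, and the partial-date rules beside it contradict it. Following it literally would place a fully dated, unworsened pre-dose AE in the TEAE tables. The effect of one such event is at most 16.7 points in a full active cohort, and about 10 to 12.5 points in pooled placebo if 8 to 10 placebo participants were enrolled. Both figures require that the event be the participant's only TEAE in the row. The direction is over-counting only.

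A reader might infer more than this. One inference is that the plan ignores onset altogether; the partial-date rules show that it does not. Another is that one event could move a placebo group of 2 by 50 points; the table layout in SAP 7.1 pools placebo across cohorts. A third is that a sizeable share of cohorts would be affected; the documents give no rate to support that, and the collection procedures suggest such events should be uncommon.

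**What to change.** In SAP 12.1:

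- Define treatment-emergent AEs as those with onset, or worsening in severity, on or after the start of the first dose. Keep the existing end of the window at the safety follow-up visit.
- Define pretreatment AEs as those with onset or worsening after ICF signature and before the start of the first dose.
- Keep the worst-case rules for partial dates as they are.
- Record the change in SAP 14.

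Align Protocol 9.4.1 only if the protocol is amended again. The SAP already records that the study ended early, so an amendment for this alone would serve little purpose.

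The cost is a few words. The SAP already uses AE start dates, so no new data are needed, and TEAE counts may fall slightly.
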